11 SAFETY ASSESSMENT AND MANAGEMENT

11.1 SAFETY PARAMETERS

Safety will be assessed by summarizing adverse events.

11.2 MEDICAL DEVICE REPORTING

The Sponsor will follow internal Standard Operating Procedures.

11.3 SAFETY DEFINITIONS

11.3.1 ADVERSE EVENT (AE)

An Adverse Event (AE) is defined as any untoward medical occurrence, whether or not related to the device or investigational procedure(s). AE's are characterized by grading, actions taken, relationship to the investigation, and outcome. These definitions are defined in the corresponding tables below.

Table 3: Adverse Event Severity Grading

Severity	Description
Grade 1: Mild	Awareness of signs or symptoms, but they are easily tolerated
Grade 2: Moderate	Enough discomfort to cause interference with usual activity
Grade 3: Severe	Incapacitating, with the inability to work or do usual activity

Table 4: Adverse Events Action(s) Taken

Action Taken	Description
None	No actions were taken
Medications	Subject required medication(s)
Other Treatment Required	Subject required other treatment(s)
Discontinued Study	Subject was discontinued from the study

Table 5: Adverse Event Relationship to Investigation

Relationship	Description
None	Causal relationship can be ruled out
Possible	Causal relationship is reasonably possible (i.e., the relationship cannot be ruled out)
Definitely	Causal relationship is certain

Table 6: Adverse Event Outcome

Outcome	Description
Death	Death was an outcome of the adverse event.

Life-Threatening	Substantial risk of dying at the time of the adverse event or use or continued use of the device or other medical product might have resulted in the death of the subject. *
Hospitalization (initial or prolonged)	Admission to the hospital or prolongation of hospitalization as a result of the adverse event. **
Disability or Permanent Damage	The adverse event resulted in a substantial disruption of a subject's normal ability to conduct normal life functions.
Congenital Anomaly/Birth Defects	Exposure to a medical product prior to conception or during pregnancy resulting in an adverse outcome in the child.
Other Serious or Important Medical Events	Checked if the event does not meet other outcomes, but the event may jeopardize the subject and may require medical or surgical intervention to prevent one of the other outcomes.
Required Intervention to Prevent Permanent Impairment/damage	The medical or surgical intervention was necessary to preclude permanent impairment of body function or prevent permanent damage to a body structure, either situation to be due to the use of a medical product.

11.3.2 SERIOUS ADVERSE EVENT (SAE)

An SAE is defined as an AE that meets any of the following criteria: Fatal or life-threatening; requires or prolongs in-subject hospitalization; results in persistent or significant disability/incapacity; congenital anomaly/birth defect; important medical event. AE's severity grading, action(s) taken, relationship to the investigation, and the outcome will all be used for SAE's.

*Whereas life-threatening is defined as an event in which the subject was at risk of death at the time of the event. It does not refer to an event that hypothetically may have caused death if the event was more severe.

**Whereas in-subject hospitalization is defined as an event in which the subject was admitted to the hospital for one or more days, even if released on the same day or an emergency room visit, which results in admission to the hospital. Emergency room visits that do not result in admission to the hospital should be evaluated for one of the other serious outcomes criteria.

11.3.3 UNANTICIPATED ADVERSE DEVICE EFFECT (UADE)

An unanticipated adverse service effect is defined by 21 CFR 812.3 as any serious adverse effect on the health or safety or life-threatening problem or death caused by or associated with a device, if that effect, problem, or death was not previously identified in nature, severity, or degree of incidence in the investigational plan or application (including supplementary plan or application, or any other unanticipated serious problem associated with the device that relates to the rights, safety, or welfare of subjects.

Table 7: Unanticipated Adverse Device Effect Subject Outcome

Outcome (check all that apply)	Description
[Redacted]	[Redacted]

Death	Death was an outcome of the adverse device effect.
Life-Threatening	Substantial risk of dying at the time of the adverse device effect or use or continued use of the device might have resulted in the death of the subject. *
Hospitalization (initial or prolonged)	Admission to the hospital or prolongation of hospitalization as a result of the adverse device effect. **
Disability or Permanent Damage	The adverse device effect resulted in a substantial disruption of a person's normal ability to conduct normal life functions.
Congenital Anomaly/Birth defects	Exposure to a medical product prior to conception or during pregnancy resulting in an adverse outcome in the child.
Other Serious or Important Medical Events	Checked if adverse device effect does not meet other outcomes, but the effect may jeopardize the subject and may require medical or surgical intervention to prevent one of the other outcomes.
Required Intervention to Prevent Permanent Impairment/damage	The medical or surgical intervention was necessary to preclude permanent impairment of body function or prevent permanent damage to a body structure, either situation to be due to the use of the device.

*Whereas life-threatening is defined as an event in which the subject was at risk of death at the time of the event. It does not refer to an event that hypothetically may have caused death if the event was more severe.

**Whereas in-subject hospitalization is defined as an event in which the subject was admitted to the hospital for one or more days, even if released on the same day or an emergency room visit, which results in admission to the hospital. Emergency room visits that do not result in admission to the hospital should be evaluated for one of the other serious outcomes criteria.

Table 8: Unanticipated Adverse Device Effect

Device Effect	Description
Death	The device effect resulted in the death of a subject
Serious Injury	The device effect resulted in Serious Injury to the subject
Malfunction	The device effect resulted in a malfunction

11.4 RECORDS

Records of events will be recorded in the source document and Case Report Form (CRF). In the instance a CRF is used as a source document, it will only be reported in the CRF.

11.5 SAFETY REPORTING

Safety reporting begins at the time of verbal Informed Consent and ends at subject study completion.

Investigators shall submit to the Sponsor and to the reviewing IRB a report of any AE's or SAE's that occur during the study within five (5) working days but no later than ten (10) days after the Investigator learns of the event.

Investigators shall submit to the Sponsor and to the reviewing IRB a report of any UADE(s) that occur during the study as soon as possible but no later than ten (10) working days after the Investigator learns of the effect. Sponsors will evaluate UADE's.

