7.2.4 OBSERVATION

The site will follow its standard operating procedure (SOP) to monitor postoperative subjects in the recovery room and PACU. The Investigator or qualified designated study personnel will continue monitoring the subject and observe the subject for at least 1 hour but no longer than 6 hours postoperatively. Any observations can be recorded (by using the mark event button on the CM-1500 device), but it is not required as all relevant events will be recorded in the patients medical records as per the SOP of the site. Observations may include but are not limited to indoor temperature of the postoperative recovery room or PACU, time and type of medication delivery, vital sign data (as obtained as part of the sites SOP), and the subject's position. Following/using the site's SOP, should the subject show signs of hemorrhage or a potentially poor outcome, the site will note this in the EMRs including time and date of the observation.

After the observation period is complete, the monitoring session will be stopped, and the electrode array sets will be removed and disposed of. Redacted medical records will be provided to the Sponsor.

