7.3 UNANTICIPATED DEVICE EFFECT (UADE)

Unanticipated Adverse Device Effect (UADE) that occurs after informed consent and before completion of the study will be recorded. UADE's may require follow-up contact via study visit, telephone call, or both depending on the nature of the UADE.

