7.4 FOLLOW-UP VISIT/CONTACT

In the event of a poor outcome due to the subject's surgery, the Investigator or qualified designated study personnel will perform follow-up contact via telephone call 7(± 5) days after the outcome occurred. The Investigator or study personal will record any follow-up attempts or contact made. Should the outcome not be resolved in 7(± 5) days, follow up might continue until resolved, or the outcome will be notated as unknown upon approval by the Sponsor.

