7.5 SUBJECT COMPLETION

A subject has completed the study when all Screening, Visit 1, and, when applicable, follow-up contact is completed and documented.

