10.2.1 RISKS: USING THE DEVICE

- [Possible, Rare] Skin irritation could occur from the electrodes

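### For subjects without a poor surgical outcome or a UADE, adverse event reporting ends at about electrode removal, so skin irritation that appears later, the one risk listed in section 10.2.1, falls outside it

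*Combined protocol and SAP*

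**What the plan says.** Section 11.5 defines the reporting period: "Safety reporting begins at the time of verbal Informed Consent and ends at subject study completion". Section 7.5 defines its end: "A subject has completed the study when all Screening, Visit 1, and, when applicable, follow-up contact is completed and documented".

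Two sections provide for contact after Visit 1. Section 7.4 links it to the operation: "In the event of a poor outcome due to the subject's surgery, the Investigator or qualified designated study personnel will perform follow-up contact via telephone", timed 7 (±5) days after that outcome. Section 7.3 adds that "UADE's may require follow-up contact via study visit, telephone call, or both depending on the nature of the UADE". Table 2 in section 7.6 follows the same pattern: adverse events are reviewed at Visit 1, and at Day 7 (±5) only if applicable.

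Electrode removal is the last act of Visit 1. Section 7.2.3 (step S19) and section 7.2.4 both place it after the monitoring session is stopped. Step S18 allows that session to last as little as 60 minutes and sets 6 hours after surgery as the limit.

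Section 10.2.1 has one entry, rated possible and rare: "Skin irritation could occur from the electrodes". Section 11.1 assesses safety by a summary of adverse events and nothing else. Section 7.2.4 also states: "Redacted medical records will be provided to the Sponsor".

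**The concern.** The follow-up rule is keyed to the surgery, while the listed risk of using the device is a skin reaction to the electrodes. Such a reaction can first show after the electrodes come off. A subject whose operation went well has by then completed the study, so the reaction is not reportable and prompts no contact.

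The adverse event summary is the study's only safety result. If some irritation appears late, that summary understates how often the device irritates skin. A reader would not know this, because the plan nowhere says that the summary stops at about removal for these subjects. Irritation already visible at removal is reportable, but no study step asks staff to look for it and write down what they see.

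**Working it through.** The plan states no figure to reproduce here, so the check is mainly a reading of the sections in sequence.

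**1. When does the window close?**
- Section 11.5: at subject study completion.
- Section 7.5: at the end of Visit 1 unless follow-up contact applies. Completion must also be documented, which could lengthen the window slightly but adds no look at the subject.
- Sections 7.2.3 (S19) and 7.2.4: Visit 1 ends with the session stopped and the electrodes removed.

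Without follow-up contact, time under observation after removal is therefore about zero.

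**2. Could irritation itself trigger contact?**
- Section 7.4 requires a poor outcome due to the surgery. Electrode irritation is not one.
- Section 7.3 requires a UADE. Section 11.3.3 limits that to serious effects, and only "if that effect, problem, or death was not previously identified in nature, severity, or degree of incidence in the investigational plan" (or application). Ordinary irritation is not serious, and section 10.2.1 already identifies it.

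Neither route is opened by the event of interest.

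**3. Is a skin check recorded at removal?**
- S19 covers removal and disposal only.
- S18 asks for adverse events during the session to be documented, and Table 2 has an adverse event review at Visit 1.
- Section 10.2.3 calls for sensor sites to be inspected for skin integrity, but as a device caution and not as a study procedure with a CRF entry.

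**4. How many subjects are affected?** Let p be the proportion who receive follow-up contact. The number without it is 200 × (1 − p). The documents give no p for mixed abdominal and pelvic surgery, so p is an assumption. The haemorrhage rates cited in section 2 are for pancreatic surgery only and serve as reference points.

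| p | Basis | Subjects without follow-up, of 200 |
|---|---|---|
| 2% | assumption | 196 (98%) |
| 5% | assumption | 190 (95%) |
| 13.6% | 68/500, section 2 | 172.8, about 173 (86%) |
| 16.82% | 18/107, section 2 | 166.4, about 166 (83%) |
| 30% | assumption | 140 (70%) |

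Most subjects close at Visit 1 at every value tried.

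**5. How large is the undercount?** Let f be the share of irritations that first appear after removal. Suppose follow-up contact catches all late cases among those contacted, and that f does not depend on who is contacted. The share missed is then f × (1 − p): 0.86f at p = 13.6% and 0.83f at p = 16.82%. The documents say nothing about f, so any percentage put on the undercount only hands back the value assumed for f. The direction is fixed: if f is above zero, the reported rate is too low.

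**The case against.** The strongest objection is that this is a reasonable design choice. The device is FDA cleared, non-invasive and classed as non-significant risk. The listed irritation is rated rare. The primary objective concerns the Relative Index, and no safety hypothesis depends on an irritation rate. Irritation seen by the time of removal is already reportable. All of this stands, and it is why the point is minor.

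A second objection concerns the remedy. A reader might infer that all adverse event capture should simply run to hospital discharge at almost no cost. The documents do not support that. Section 11.3.1 counts any untoward medical occurrence, related or not, and section 11.5 sends each one to the sponsor and the IRB. Running the whole window to discharge would make every post-operative event in up to 200 surgical patients reportable. Section 7.2.4 does not say what period the supplied records cover, the protocol gives no length of stay, and mild irritation may not be charted. Section 15.2 rests the waiver of consent documentation partly on very limited health information being collected. This objection succeeds against a general extension, but not against a recorded look at removal and a narrow extension within records already supplied.

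Three other stronger readings should be resisted:
- **Nearly all subjects are affected.** That needs p of about 5% or less, which the documents do not establish for this population. The safe statement is every subject without a poor surgical outcome or a UADE.
- **Irritation is the only device hazard named.** It is the only entry in section 10.2.1, but section 10.2.2 warns of burns at the electrodes and section 10.2.3 of tissue damage from incorrect sensor use.
- **The report would quote a misleading upper bound.** With no events in 200, a one-sided 95% bound would be 1 − 0.05^(1/200) = 1.49%, but the plan specifies no such interval. A reader who calculates one should take it as covering essentially irritation evident by removal.

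**Conclusion.** The point holds as a minor one. For every subject without a poor surgical outcome or a UADE, safety reporting ends with Visit 1, at about electrode removal. Irritation that first appears later is outside the window by rule, and no skin check is recorded at removal.

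The affected group would be 83% to 86% of subjects if follow-up occurred at the haemorrhage rates the protocol cites for pancreatic surgery, and 70% to 98% over the assumed range of 30% down to 2%. The undercount itself cannot be sized from the documents. That there is one rests on a single assumption: that some irritation appears only after the electrodes are off. The Relative Index objective is not affected.

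**What to change.** 1. **Section 7.2.3, step S19:** add an inspection of the wrist and neck/shoulder electrode sites at removal, with the finding recorded on the CRF whether or not anything is seen.
2. **Section 11.5:** after Visit 1, continue capture for device-related electrode- or sensor-site events only, as far as the medical records already supplied to the sponsor extend. State that general post-operative adverse event reporting still ends at completion.
3. **Adverse event summary (section 11.1):** state that site reactions with onset after removal are not systematically captured.

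The cost is one CRF line and slightly more record abstraction, with no added subject contact. Staff are already at the bedside removing the electrodes. The reported device-related event rate may rise slightly. If the records stop soon after Visit 1, the second change will yield little; the third covers what remains.

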12 STATISTICAL METHODS AND CONSIDERATIONS

12.1 SAMPLE SIZE DETERMINATION

The sample size of up to 200 subjects was determined feasible.

12.2 DATA SETS ANALYZED

All eligible subjects who completed Screening and used the device will be included in the analysis. Subjects who withdraw after Screening and before device use will be excluded.

12.3 DEMOGRAPHIC AND BASELINE CHARACTERISTICS

The following will be summarized: age, sex, race, ethnicity, height, and weight.

12.4 STATISTICAL ANALYSIS PLAN (SAP)

The majority of evaluations pertaining to the performance of the CM-1500 device will examine the behavior the Relative Index value in accordance with subject outcomes and conditions that present following operatory procedures. The SAP however, can include

investigation into individual vital sign parameters that the CM-1500 device (or another source) produces during a subject's recovery.

Analysis of data sets collected from all subjects aim to satisfy the following purposes, included but not limited to:

- Examine, on a case by case review basis, the results produced by the CM-1500 device for relevant subject case results.

- Classify aggregate results by subject outcomes, particularly nominal and hemorrhagic shock/complications, and evaluate the performance of the CM-1500 to indicate either the presence of the presenting complication, or specify the absence of presenting complications.

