2 INTRODUCTION

Postoperative hemorrhage incidence can vary depending on the type of surgery, but it can lead to severe clinical complications ranging from mild anemia to fatal hemorrhagic shock. One study conducted by Mañas-Gómez et al. (2011) evaluated 107 post-pancreaticoduodenectomy (PD) patients between January 2005 and December 2008 and found that 16.82% (18/107) patients hemorrhaged after PD. Of those, four (4) of the eighteen (18) patients hemorrhaged early (< 24 hours).¹ The study also found that hemorrhage after pancreatic resection may be considered a complication with a high mortality rate. Ansari et al. (2016) conducted a retrospective observational study on 500 consecutive patients undergoing major pancreatic resections.² The study found that 13.6% (68 patients) developed post-pancreatectomy hemorrhage.²

Monitoring and detecting these fluid changes postoperatively can be complicated, and standard operating procedures vary. The Cardiac Monitor, Model 1500 (CM-1500), uses a personalized approach by non-invasively and simultaneously monitoring five (5) physiological parameters, including bioelectrical impedance, ECG Amplitude, PPG Amplitude, heart rate, and skin temperature. [REDACTED]

[REDACTED] When the monitoring session starts, each patient starts with a Relative Index of 100 signifying parameters near their original baseline value. The Relative Index value acts as a combinational score [REDACTED]

[REDACTED]

[REDACTED]

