10 RISKS & BENEFITS

10.1 RISK DETERMINATION

This investigation is a Pivotal study that is determined to be an non-exempt, non-significant risk investigation. An Investigational Device Exemption (IDE) will be submitted based on this determination. The device will be used as intended and no clinical decisions will be made based off of the information obtained.

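### Section 12.4 sets a device-performance aim but fixes no Relative Index summary, direction, cut-point, window or metric; with few in-session bleeds, choices made after outcomes are known can easily look discriminating by chance

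*Combined protocol and SAP*

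**What the plan says.** Section 3.1 makes change in the RI the primary objective. Section 12.4 says most performance evaluations will "examine the behavior the Relative Index value in accordance with subject outcomes", then classify subjects by outcome, mainly uneventful recovery versus hemorrhagic shock or complications, and "evaluate the performance of the CM-1500 to indicate either the presence of the presenting complication" or its absence.

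Section 12.4 also permits "investigation into individual vital sign parameters that the CM-1500 device (or another source) produces during a subject's recovery", and states that its list of purposes is not exhaustive. It defines no bleed case and gives no RI summary (minimum, change, slope, time below a level), direction, cut-point, window, accuracy measure, interval or validation step. Sections 12.1 to 12.3 do not supply these. On size, 12.1 says only: "The sample size of up to 200 subjects was determined feasible".

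Section 7.2.3 sets the monitoring session at 60 minutes up to 6 hours after surgery. Section 7.2.4 has signs of hemorrhage noted in the medical record with date and time. Section 10.1 states: "This investigation is a Pivotal study".

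**The concern.** An aim of showing how well a device indicates a complication is a diagnostic-accuracy aim. If the RI summary, its direction or the cut-point is settled after the analyst can see who bled, sensitivity and specificity computed on the same subjects are biased upward. The bias grows as events become fewer and as more signals are tried, and it cannot be undone once the data have been seen. In a study called pivotal, an index that carries no information could be reported as useful.

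The RI summary matters as much as the cut-point. Sessions may last from 1 to 6 hours, so a session-long minimum, for example, has more time to fall in some subjects than in others.

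**Working it through.** **Inputs from the documents.** N is up to 200 (12.1). The Introduction's pancreaticoduodenectomy series reports 18/107 bleeds, of which "four (4) of the eighteen (18) patients hemorrhaged early (< 24 hours". The pancreatic resection series reports 68/500. Session length is 1 to 6 h (7.2.3). The device gives "five (5) physiological parameters, including bioelectrical impedance, ECG Amplitude, PPG Amplitude, heart rate, and skin temperature", so with the RI there are 5 + 1 = 6 device signals.

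**Plan's own figures.** 18/107 = 16.82% and 68/500 = 13.6%; both reproduce. Section 12.1 gives no alpha, power, event rate or precision target, so there is no sample-size calculation to reproduce.

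**Expected bleeds.** Assumptions: the 4/107 rate applies to all abdominal and pelvic surgery, the hazard is constant over 24 h, and all 200 are enrolled.
- 24 h: 200 × 4/107 = 7.5.
- 6 h: 7.5 × 6/24 = 1.9. One hour: 7.5 × 1/24 = 0.3.
- The exact 95% interval for 4/107 is 1.0% to 9.3%, which gives 2.1 to 18.6 bleeds in 24 h and 0.5 to 4.6 in 6 h.
- At the 6 h rate (0.93%), P(0 bleeds) = (1 − 0.00935)^200 = 15% and P(at most 1) = 44%.
- Bleeds at any time, at the two cited rates: 200 × 13.6% = 27 and 200 × 16.82% = 34.

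**Chance discrimination.** Simulated: N = 200, signals unrelated to bleeding, and for each signal the cut-point that maximises Youden's J = sensitivity + specificity − 1. The six signals are independent unless stated.

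| Bleeds | One signal, fixed direction: mean J; P(J ≥ 0.5) | Best of six, fixed direction: mean J; P(J ≥ 0.5) | Best of six, either direction: P(J ≥ 0.5) |
|---|---|---|---|
| 2 | 0.38; 26% | 0.67; 83% | 99% |
| 7 | 0.22; 2% | 0.38; 12% | 24% |

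With 4 bleeds, P(J ≥ 0.5) is 10%, 49% and 73% across the same three columns. If the six signals are correlated at 0.5 and either direction is allowed, it is 96%, 64% and 20% for 2, 4 and 7 bleeds. With 27 to 34 bleeds it is essentially zero; the median best J of six signals in either direction is then 0.22 to 0.24.

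**With one signal, direction and cut-point fixed at 80% specificity.** A useless signal has expected J of 0. It detects both of 2 bleeds with probability 0.2² = 4%, and at least 6 of 7 with probability 7 × 0.2⁶ × 0.8 + 0.2⁷ = 0.04%.

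**Precision that remains (Clopper-Pearson 95%).** Sensitivity for 2/2 detected: 16% to 100%. For 4/4: 40% to 100%. For 5/7: 29% to 96%. For 7/7: 59% to 100%.

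**The case against.** The strongest reply is that the plan is less open than it looks. The RI is the named signal in 3.1 and 12.4, and individual parameters are an optional addition. That stands: what is open is the RI summary, its direction and the extra signals, not the choice of the RI itself.

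A reader might infer that 12.4 tells the analyst to choose a cut-off from the data. It does not; it mentions no cut-off, sensitivity or specificity. Its silence leaves that route open without prescribing it.

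A reader might also infer that no threshold exists. Text about the RI is redacted in sections 2, 4.1, 4.2 and 7.2.3, and a threshold or direction may sit there. But 12.4 shows no redaction and refers to no threshold. A documented threshold would need only a cross-reference, though it would not in itself supply the accuracy metric or interval.

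Finally, the event count is uncertain in both directions. The rate comes from pancreatic surgery while any abdominal or pelvic surgery is eligible, so the in-session count could be lower. The figure of 7.5 is a 24 h count that runs past the session. Counting later bleeds or wider complications would raise the number and shrink the problem. This also stands, and it is why the counts above are illustrations; 12.4 does not say which events count.

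**Conclusion.** The point holds in limited form. Section 12.4 states a performance aim in a study labelled pivotal, and its visible text leaves unfixed every element that determines apparent accuracy, apart from naming the RI as the main signal.

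The conclusion that false discrimination will occur is not supported. It is near certain only with about 2 bleeds and a search over several signals in either direction (P(J ≥ 0.5) of 96% to 99%). For one signal in a fixed direction with 7 bleeds, that probability is about 2%. The supported statement is that such a result can easily arise by chance when bleeds are few and several signals are tried. About 1.9 in-session bleeds is the central illustration. It rests on a borrowed rate, a constant hazard and full enrolment, and it is an upper-end session figure because sessions may be as short as 1 h.

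**What to change.** Amend 12.4 before any RI file is linked to outcomes:

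1. Name one primary RI summary, its direction and its time window.
2. Define a bleed for the analysis, for example hemorrhage noted in the medical record during the session, using the noted time.
3. Report the AUC of that summary. Report sensitivity and specificity only at a cut-point fixed in advance, with Clopper-Pearson intervals. If the device documentation contains a threshold, cite it.
4. Label every other signal and any data-derived cut-point exploratory, and base no performance claim on them.
5. State a minimum number of in-session bleeds. Below it, give descriptive case listings only, with no AUC or bootstrap interval. With 2 bleeds in 200, (198/200)^200 = 13% of ordinary bootstrap resamples contain no bleed, and with none the AUC is undefined. The exact lower limits when every bleed is detected (16% at 2, 40% at 4, 59% at 7) can guide the choice.

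The cost is SAP wording and a little programming, with no added subjects or procedures. Headline accuracy may look less favourable and the intervals will be wide: pre-specification removes the selection bias and leaves the imprecision.
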